4.1 Inclusion Criteria

- Males between ages 13-30 (inclusive) at the time of the consent
- Subject is capable of giving written informed consent or has a legally authorized representative (LAR) with sufficient intellectual capacity to provide written informed consent on the patient's behalf. For subjects that do not have sufficient capacity to provide informed consent, written informed assent will be obtained when developmentally appropriate.
- Subject has a reliable informant (parent or caregiver) who has sufficient past and current knowledge of the subject and will oversee the administration of study medication and accompany the subject to each study visit.
- Subject and caregiver have reliable means of transportation to attend study visits.
- Primary diagnosis of Autism Spectrum Disorder (ASD) severity level 2 or 3, confirmed by *Diagnostic and Statistical Manual-5* (DSM-5) criteria (as assessed by the PI, a physician experienced in the diagnosis of ASD) and meeting the autism cut-off score of 8 or greater on the Autism Diagnostic Observation Schedule-2 (ADOS-2) (conducted by a master's level

sub-investigator with extensive experience in administration of the ADOS-2) at the time screening

4.2 Exclusion Criteria

- Caregiver is unable to proficiently speak and understand English
- The subject is unable to ingest the study tablets orally, either by swallowing whole or crushing and mixing in a small amount of a soft food (e.g., applesauce, yogurt).
- Chronic medical illness that is not stable, would pose a risk to the participant if he participates in the trial, or would otherwise confound results (e.g. autoimmune disorders).
- A history of seizure within the 12 months preceding study enrollment
- Changes to psychopharmacological medications (e.g., stimulants, antidepressants, anxiolytics, antipsychotics) in the 2 weeks preceding study enrollment
- Significant changes to non-pharmacological treatments in the 4 weeks preceding study enrollment (e.g., starting a new behavioral therapy program)
- Chronic treatment with anti-inflammatory agents (e.g., ibuprofen, NSAIDs, corticosteroids)
- Clinically significant laboratory abnormalities at Screening visit (e.g., AST/ALT> two times the upper normal limits; serum creatinine > 1.2 mg/dl, TSH outside normal limits)
- Clinically significant findings on physical examination that investigator determines could increase risk of harm from participating in the study
- Participated in another clinical interventional trial or received an investigational product in the 30 days preceding study enrollment
- Previous therapeutic trial of sulforaphane or participation in a clinical trial in which sulforaphane was the investigational agent

4.3 Subject Recruitment and Screening

Subjects will primarily be recruited from the Carolina Institute for Developmental Disabilities (CIDD) Research Subject Registry, which includes more than 6000 families that have expressed an interest in research participation and have consented to be contacted about potential studies. Potential subjects will be contacted directly via email or letter by the Registry staff with information about the trial, including contact information of study staff. Participants will also be recruited from the clinical practices of physicians, psychologists, and allied health staff at the Carolina Institute for Developmental Disabilities as well as from local referring providers. Electronic and written advertisements will be disseminated to local community autism support agencies (e.g., Autism Society of North Carolina, Autism Resource Centers). All recruitment materials will first be approved by the University of North Carolina IRB.

Potential subjects expressing an interest in study participation will go through an initial telephone screening process to assess eligibility for study participation (e.g., previous autism diagnosis, male, ages 13-30, able to be accompanied by a caregiver who can serve as a primary informant, not taking chronic anti-inflammatory medication, free of major medical illness, no clinical seizures in the previous 12 months). Before the initial clinic screening visit, the caregiver and subject will be sent a copy of the informed consent form for review.

Written informed consent by a caregiver will be obtained before proceeding with all screening assessments. Whenever possible, informed assent will also be obtained from the participant. The study will pilot a tablet-based electronic decisional capacity tool developed at Research Triangle Institute (RTI) International to enhance participation in the assent process for individuals with developmental disabilities. Prior to study enrollment, participants will undergo diagnostic confirmation of autism spectrum disorder at the screening visit by review of DSM-5 Autism Spectrum Disorder (ASD) criteria (by the study PI) and by *Autism Diagnostic Observation Schedule-2* administration (by a master's level clinician experienced in ADOS-2 administration for research purposes). Screening requirements will also include routine laboratory testing (CBC, electrolytes, LFTs, TSH), medical history, and physical examination to identify any exclusionary factors. Screening laboratory values and physical exam findings must be within normal limits or deemed not clinically significant by the study physician prior to study enrollment. Subjects with serious medical illnesses that are poorly controlled, that may increase risks associated with study participation, or that may otherwise confound results will not be enrolled.

4.4 Early Withdrawal of Subjects

4.4.1 When and How to Withdraw Subjects

Subjects will be withdrawn from *study* participation only if the subject or his legal authorized representative revokes consent for inclusion of subject data in group analyses.

Reasons for *treatment* withdrawal prior to the expected completion for a subject may include:

- The subject experiences a serious adverse event (SAE) that the study physician determines is likely related to the study treatment or that presents a safety risk for ongoing participation.
- The subject experiences a clinical seizure during the course of the active treatment phase, either by EEG confirmation or by strongly suggestive clinical history.
- The subject requires significant dose adjustments to concomitant psychopharmacological medications (e.g. stimulants, antidepressants, mood stabilizing agents, benzodiazepines) or starts a new psychopharmacological medication due to significantly worsened behavioral disturbance.
- The subject requires a new chronic medication that may potentially interact with the study medication.

No withdrawal symptoms or adverse effects are anticipated from abrupt discontinuation of the study medication. However, if a patient needs to discontinue the study treatment for one of the aforementioned reasons, every effort will be made to bring the subject in promptly for a clinic visit to perform safety measures, including physical examination and laboratory measures. As described below, study personnel will request that subjects who prematurely stop treatment complete the remaining study visits and procedures as outlined in the protocol.

4.4.2 Data Collection and Follow-up for Withdrawn Subjects

If a subject withdraws from treatment prematurely, every effort will be made to obtain the subject/ caregiver's permission to collect data through the end of the planned subject follow-up period (week 16 visit). The data collected will be included in the final data set under intention-to-treat analysis, provided the participant took at least 1 dose of study medication and attended at least 1 post-baseline assessment.

If a subject appears lost to follow-up, study personnel will attempt to reach the subject's caregiver by all provided telephone numbers and email addresses on two occasions each. If the caregiver cannot be reached by phone or email, a certified letter will be sent requesting that the caregiver contact the study personnel to further discuss the subject's involvement in the trial. A second certified letter will be sent two weeks after the first letter was sent if the subject's caregiver has not responded within those two weeks. If the caregiver does not respond to the second letter, the subject will be considered lost to follow-up. All attempts to contact the subject's caregiver will be documented in a communication log.

5 Study Drug

5.1 Description

The investigational agent is supplied as a white, flecked, uncoated tablet. Each active tablet will contain 125 mg broccoli seed extract powder (equivalent to approximately 36 μ mol GR), 50 mg broccoli sprout extract powder (source of myrosinase), 15 mg ascorbic acid, 7.5 mg carboxymethylcellulose, 6.5 mg silicon dioxide, and 171 mg microcrystalline cellulose. The placebo tablets will be similar in shape, size, and color.

5.2 Treatment Regimen

Participants will take 3-8 Avmacol[®] or placebo tablets once daily by mouth for a total of 12 weeks, with dosing regimen based on weight as follows:

3 tablets (approx. 46.5 μ mol SF) if <100 lb 5 tablets (approx. 77.5 μ mol SF) if 100-125 lb 6 tablets (approx. 93 μ mol SF) if 126-175 lb 7 tablets (approx. 108.5 μ mol SF) if 176-199 lb 8 tablets (approx. 124 μ mol SF) if \geq 200 lb

The tablets may be crushed and mixed with a soft food, such as applesauce, if needed. Participants will be instructed to avoid taking the tablets with a heavy meal.

5.3 Method for Assigning Subjects to Treatment Groups

Enrolled participants will be stratified for age (13-18 and 19-30 years) to account for possible effects of age on treatment response. The goal is to recruit twenty-seven 13-18 year-olds and twenty-seven 19-30 year-olds to allow for separate analysis of adolescents and adults (exploratory). Individuals will be randomly assigned to treatment group within age strata by generating random numbers for each group for each entry (i.e., 1-27 for younger group and 1-27

for older group). The larger half of the random numbers within each group will be assigned to receive the treatment and the smaller half to the placebo condition. These two lists – listed in their original order (1-27 for younger and 1-27 for older) will be provided to UNC Investigational Drug Services (IDS) pharmacists. They will consult the list and provide the appropriate medication to each individual depending on the order in which they present to the pharmacy within their age group. Study personnel will remain blinded to treatment condition for the duration of the study.

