3.1 General Design

We propose to conduct a Phase II, randomized, double-blind, placebo-controlled trial of Avmacol®, a rich source of sulforaphane, for the treatment of social impairment in individuals with ASD. Fifty-four male subjects with autism spectrum disorder (ASD) between ages 13 and 30 years old will be randomized in a 1:1 ratio, stratified by age category (13-18 and 19-30 years old), to receive either Avmacol® or identical placebo tablets. Participation will be limited to males to closely approximate the sample used in the SF for ASD clinical trial by Singh et al. [48] and to account for possible mechanistic differences in ASD between males and females (ASD is 4 times more common in males). Stratification by age will account for possible age-based differences in response to treatment (adolescence vs. adulthood) and allow for secondary analysis by age group (adolescent vs. adult).

The length of study participation from baseline to study termination for each individual subject is 16 weeks, including a 12-week active treatment phase (Avmacol® or placebo), followed by a 4-week blinded discontinuation phase. Participants will be monitored with clinic visits at regular intervals (baseline and weeks 4, 8, 12, and 16) for improvement in a well-characterized, caregiver-rated measure of social impairment (Social Responsiveness Scale-2 (SRS-2) [100], the primary outcome) as well as secondary measures of (1) repetitive behaviors associated with ASD (Repetitive Behavior Scale- Revised; RBSR) [102]; (2) challenging behaviors commonly associated with developmental disabilities (Aberrant Behavior Checklist; ABC) [103]; (3) clinician-rated functional severity (Clinical Global Impression Scale- Severity; CGI-S) [104]; and clinician-rated functional improvement (Clinical Global Impression Scale- Improvement; CGI-I) [104].

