7.1 Sample Size Determination

We calculated power for comparing groups on change in SRS-2 total score (the primary outcome measure), using a standard approach for linear mixed models (Littell RC, Milliken GA, Stroup WW, Wolfinger RD, Schabenberger O. *SAS for mixed models [electronic resource]*. Cary, N.C.: SAS Institute, Inc.; 2006). We assumed that the mean differences observed in the trial by Singh et al. represented the true values (i.e., we assumed mean differences of 7, 20, 18.4, and 0.4 at weeks 4, 8, 12 and 16, respectively), and we assumed a constant standard deviation of 20, consistent with that observed by Singh et al. Furthermore, we assume within-participants across time correlation of 0.5 (a conservative value) and we assume no more than 15% loss distributed over the 16 weeks of follow-up. Under these assumptions, randomizing 27 participants to each group will provide at least 80% power for an overall test comparing groups across all time points using a two-sided 4 degree of freedom test at the 0.05 significance level.

For the exploratory microbiota analysis, we aim to include a subset of 30 subjects in the sample. In a recent randomized cross-over trial of the effects of broccoli consumption on microbiota composition in 18 healthy adults [Kaczmarek 2017*], participants consuming broccoli exhibited an increase in the ratio of Baceteroidetes to Firmicutes by 37% from baseline to end, compared to a 5% reduction during the control period (p=0.02). With 15 participants per group, we will have >80% power to detect a similar change in the ratio of Bacteroidetes to Firmicutes.

* Kaczmarek JL, et al. Broccoli consumption impacts the human gastrointestinal microbiota. The FASEB Journal, 2017. 31(1 suppl): p.965.

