Subjects will primarily be recruited from the Carolina Institute for Developmental Disabilities Research Subject Registry, which includes more than 6000 families that have expressed an interest in research participation and have consented to be contacted about potential studies. Potential subjects will be contacted directly via email or letter by the Registry staff with information about the trial, including contact information of study staff. Participants will also be recruited from the clinical practices of physicians, psychologists, and allied health staff at the Carolina Institute for Developmental Disabilities as well as from referring providers. Electronic and written advertisements will be disseminated to local community autism support agencies (e.g., Autism Society of North Carolina, Autism Resource Centers). All advertisement materials will first be approved by the University of North Carolina IRB.

Enrolled participants will be stratified for age (13-18 and 19-30 years) to account for possible effects of age on treatment response. The goal is to recruit twenty-seven 13-18 year-olds and twenty-seven 19-30 year-olds to allow for secondary analysis by age group. Individuals will be randomly assigned to treatment group within age strata by generating random numbers for each group for each entry (i.e., 1-27 for younger group and 1-27 for older group). The larger half of the random numbers within each group will be assigned to receive the treatment and the smaller half to the control condition. These two lists – listed in their original order (1-27 for younger and 1-27 for older) will be provided to UNC Investigational Drug Services (IDS) pharmacists. They will consult the list and provide the appropriate medication to each individual depending on the order in which they present to the pharmacy within their age group. Study personnel will remain blinded to treatment condition for the duration of the study.

During the course of the study, participants will take 3-8 Avmacol[®] or placebo tablets once daily by mouth for a total of 12 weeks, with dosing regimen based on weight as follows:

3 tablets (approx. 46.5 μ mol SF) daily if <100 lb 5 tablets (approx. 77.5 μ mol SF) daily if 100-125 lb 6 tablets (approx. 93 μ mol SF) daily if 126-175 lb 7 tablets (approx. 108.5 μ mol SF) daily if 176-199 lb 8 tablets (approx. 124 μ mol SF) daily if \geq 200 lb

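### The plan stratifies because response may differ by age, but the only age-group method it names is separate analysis of about 27 adolescents and 27 adults, which does not test that difference

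*Combined protocol and SAP*

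**What the plan says.** Section 3.1 (General Design) gives two reasons for stratifying by age: response to treatment may differ between adolescents and adults, and the design should "allow for secondary analysis by age group (adolescent vs. adult"). Section 5.3 sets a recruitment goal of 27 per stratum "to allow for separate analysis of adolescents and adults (exploratory"). Appendix 6B (part I.a) repeats the goal of 27 and 27 "to allow for secondary analysis by age group". The same work is therefore called secondary in two places and exploratory in one. Only section 5.3 names a method.

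Section 7.2 models SRS-2 total score on treatment, time and treatment phase, with their interactions, and adds age stratum and the screening SRS-2 score as covariates. No interaction involves age. Sections 7.1 to 7.3 do not describe the age-group analysis, its power, or the basis for concluding that the age groups differ.

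**The concern.** Whether response differs by age is a question about effect modification. An analysis within one stratum compares active with placebo in that stratum and says nothing directly about the other. One significant and one non-significant result is not evidence that the two effects differ, and with about 13 or 14 subjects per arm such a split is common by chance. At stake is a report that the product works only in adolescents, or only in adults, when the effect is the same in both. The interaction that addresses the question can be estimated from data the trial already collects.

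**Working it through.** **Inputs (section 7.1 unless noted).** "mean differences of 7, 20, 18.4, and 0.4 at weeks 4, 8, 12 and 16, respectively"; "we assumed a constant standard deviation of 20"; "within-participants across time correlation of 0.5 (a conservative value"); loss of at most 15%; a "two-sided 4 degree of freedom test at the 0.05 significance level". From section 5.3, 27 per stratum, hence 14 v 13 per arm, or about 12 v 11 after 15% loss. I take 20 as the SD of the score at a visit. The text could also mean the SD of change, in which case the adjusted figures in step 3 do not apply directly.

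**1. The plan's own power.** The claim is "randomizing 27 participants to each group will provide at least 80% power". With d = (7, 20, 18.4, 0.4) and S having 400 on the diagonal and 200 off it, d′S⁻¹d = 1.841. The noncentrality is 1.841 / (1/n₁ + 1/n₂).
- 27 per arm: 1.841 × 13.5 = 24.85; power 98.9% (chi-square) or 98.0% (F).
- 23 per arm: 1.841 × 11.5 = 21.17; power 97.3% or 95.3%.

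The claim holds as a lower bound. It concerns the full sample, not the strata.

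**2. Separate Week 12 tests, same true effect of 18.4 in both strata, unadjusted.** SE = 20·√(1/n₁ + 1/n₂). Power p comes from the noncentral t. The chance that exactly one stratum is significant is 2p(1−p).
- 14 v 13: SE 7.70, noncentrality 18.4/7.70 = 2.39, p = 0.632; 2 × 0.632 × 0.368 = 46.5%.
- 12 v 11: SE 8.35, noncentrality 2.20, p = 0.557; 2 × 0.557 × 0.443 = 49.4%.

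A simulation of 200,000 trials gave 46.4% and 49.6%.

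**3. The same, adjusted for pre-treatment SRS-2 at correlation 0.5** (one degree of freedom lost per covariate).

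| Adjustment | Residual SD | p, 14 v 13 | Exactly one significant | p, 12 v 11 | Exactly one significant |
|---|---|---|---|---|---|
| One score | 20·√(1 − 0.25) = 17.3 | 0.754 | 37% | 0.678 | 44% |
| Screening and baseline | 20·√(1 − 1/3) = 16.3 | 0.800 | 32% | 0.726 | 40% |

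**4. Other cases.**
- No effect in either stratum: 2 × 0.05 × 0.95 = 9.5%.
- Effect of 10 points, unadjusted: 36% without loss, 33% with loss.
- SD 15: 23% and 32%. SD 30: 45% and 41%.
- The 4-df test in each stratum: 30% (chi-square) to 40% (F) without loss, 38% to 47% with loss.

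**5. Interaction test.** It declares a false age difference in 5% of trials whatever the common effect (simulated 4.9-5.0%). Its unadjusted SE is 20·√[2(1/n₁ + 1/n₂)].
- 14 v 13: SE 10.9; 95% CI ±1.96 × 10.9 = ±21; power 39% for an 18.4-point difference between age groups.
- 12 v 11: SE 11.8; ±23; power 34%.

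For 80% power the age groups would have to differ by about 31 to 33 points.

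**The case against.** A reader might infer that the plan intends to judge age effects by comparing two p-values in preference to an interaction. The documents do not support that. Section 5.3 speaks only of separate analysis. No text says that stratum p-values will decide anything, and separate estimates with confidence intervals would satisfy the wording. Section 3.1 and Appendix 6B name no method and are compatible with an interaction. This stands: the plan is silent on the inference, so the rates above describe what follows if the results are set side by side, not what the plan prescribes.

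The analysis is also already called exploratory where its method is named, and it does not appear among the objectives, endpoints or hypotheses, so no confirmatory claim rests on it. That lowers the importance but does not make two separate tests answer a comparison, and the other two places say secondary.

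The unadjusted 46-49% is close to the 50% maximum of 2p(1−p), and section 7.2 does adjust for the screening score. That is fair, and the range of 32-44% should be quoted beside it. Finally, an interaction in 54 subjects is imprecise and could seldom confirm a real age difference. That is also true, and it is the reason to report an estimate with its interval and not only a test.

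**Conclusion.** The point holds as a minor one. As written, the plan raises the question of age-dependent response but contains no analysis that compares the treatment effect between strata. If the stratum results were read against each other, a split in significance despite identical effects would be common: about 46-49% unadjusted and 32-44% adjusted, at the planned 18.4 points, against 5% for an interaction test. These figures rest on a real common effect of the planned size, SD 20, correlation 0.5 for the adjusted range, and strata that reach their goal of 27. With no effect in either group the figure is 9.5%. They are not the probability that the trial will make a false age claim, because the documents never say that a split would be interpreted in that way.

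**What to change.** Leave the primary model in section 7.2 unchanged. Adding the interaction there could, under ordinary reference coding, turn the main effect of treatment into the effect in one age stratum.

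Specify a separate exploratory model on all randomized subjects in the section 7.3 analysis population. Cross age stratum with treatment and with the time and phase terms of section 7.2. With time centered at Week 12 and phase coded 0 during treatment, the treatment-by-age-stratum coefficient is the age difference in effect at the end of treatment. Report it with its 95% CI, together with both stratum-specific effects from the same model. State that no age-specific conclusion will be drawn from separate stratum p-values, and that a non-significant interaction does not show equal effects. Use exploratory in sections 3.1 and 5.3 and in Appendix 6B.

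The cost is wording and some extra terms in a secondary fit. Treatment, time and phase fully crossed give 2³ = 8 fixed coefficients including the intercept. Crossing these with age adds 8, of which the age term is already present, so 7 are new. Sample size, visits and data collection do not change. The price is an openly wide interval.
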